8.4. Treatment of Overdose

For the purposes of this study, an overdose of NG is considered any dose higher than the planned 3 mg dose.

In case of suspected overdosing, serum potassium levels may decrease and should be monitored and corrected if needed. If the participant develops a marked increase in blood pressure, blood pressure medication appropriate to the child's age may be administered, e.g., phentolamine mesylate for children aged 3+ years (OraVerse USPI, 2018; Baqsimi USPI, 2019).

Refer to the Product Label for additional details.

8.5. Pharmacokinetics

At the times specified in the SoA, venous blood samples of approximately 2 mL each will be collected to determine the plasma concentrations of glucagon.

Instructions for the collection and handling of blood samples will be provided by the sponsor. The actual date and time (24-hour clock time) of each sampling will be recorded. Sites may use topical anesthetics to minimize pain or discomfort associated with sample collection.

8.5.1. Bioanalysis

Samples will be analyzed at a laboratory approved by the sponsor and stored at a facility designated by the sponsor.

Concentrations of glucagon will be assayed using a validated liquid chromatography with tandem mass spectrometry method.

Bioanalytical samples collected to measure investigational product concentrations will be retained for a maximum of 1 year following last participant visit for the study.

8.6. Pharmacodynamics

At the times specified in the SoA, blood samples will be collected for use in a study-approved rapid glucose analyzer (YSI or equivalent) to determine the plasma concentrations of glucose.

Instructions for the collection and handling of blood samples will be provided by the sponsor. The actual date and time (24-hour clock time) of each sampling will be recorded.

8.7. Genetics

Genetics will not be evaluated in this study.

8.8. Biomarkers

Biomarkers will not be evaluated in this study.

8.9. Immunogenicity Assessments

Not applicable.

8.10. Health Economics

Not applicable.

9. Statistical Considerations

9.1. Statistical Hypotheses

Not applicable.

9.2. Sample Size Determination

At least 9 participants with an approximate maximum of 20 may be enrolled so that 6 evaluable participants complete the study.

The sample size is customary for Phase 1 studies evaluating safety, tolerability, PD, and PK, and is not powered on the basis of statistical hypothesis testing.

The sample size assumes a 33% dropout rate.

Participants who are enrolled but not administered treatment may be replaced to ensure that enough participants may complete the study.

9.3. **Populations for Analyses**

A detailed description of participant disposition will be provided.

The participants' baseline characteristics and demographics will be obtained at entry and will be summarized for all enrolled participants who proceed to the dosing visit.

9.4. Statistical Analyses

Statistical analysis of this study will be the responsibility of Lilly or its designee.

Any change to the data analysis methods described in the protocol will require an amendment ONLY if it changes a principal feature of the protocol. Any other change to the data analysis methods described in the protocol, and the justification for making the change, will be described in the SAP and/or in the clinical study report.

All data will be entered, verified, and archived at a CRO external to Lilly and/or at Lilly. Data listings, summaries, and analyses will be performed by a CRO and/or by Lilly under the guidance and approval of statisticians at Lilly.

Unless otherwise specified, efficacy analyses will be conducted on all enrolled participants who receive the study drug and have an evaluable efficacy outcome (based on PD parameters, see Section 9.4.3).

PK and PD analyses will be conducted on data from all enrolled participants who receive the study drug and have evaluable PK or PD data. See Section 9.4.2 for definitions of evaluable PD and PK data.

Safety analyses (Section 9.4.1) will be conducted for all enrolled participants who receive at least 1 dose of the study drug, whether or not they complete all protocol requirements.

Additional exploratory analyses of the data will be conducted as deemed appropriate.

9.4.1. Primary Endpoint: Safety

9.4.1.1. Clinical Evaluation of Safety

All investigational product and protocol procedure AEs will be listed, and if the frequency of events allows, safety data will be summarized using descriptive methodology.

The incidence of symptoms will be presented by severity and by association with investigational product as perceived by the investigator. Symptoms reported to occur prior to enrollment will be distinguished from those reported as new or increased in severity during the study. Each symptom will be classified by the most suitable term from the Medical Dictionary for Regulatory Activities.

The number of investigational product-related SAEs will be reported.

Nasal/respiratory and anosmia AEs will be identified using preferred terms and summarized. The details will be provided in the SAP.

9.4.1.2. Statistical Evaluation of Safety

Safety parameters that will be assessed include safety laboratory parameters and vital signs. The parameters will be listed or summarized using standard descriptive statistics. Additional analysis will be performed if warranted upon review of the data. Details will be provided in the SAP.

9.4.2. Secondary Endpoints: Pharmacodynamics and Pharmacokinetics

9.4.2.1. Pharmacodynamics

9.4.2.1.1. Pharmacodynamic Parameter Estimation

Due to limited number of PG measurements (5 time points), a limited number of PD parameters will be estimated. The primary PD parameter is change from baseline of BGmax. In addition, other PG parameters, BGmax, AUC, and TBGmax may also be estimated. Actual sampling times will be used for all calculations.

Baseline PG concentrations will be calculated from samples obtained immediately prior to glucagon dosing (e.g., predose).

Other PD parameters of PG may be calculated if required. Individual concentrations and PD parameters of PG will be summarized using descriptive statistics.

9.4.2.1.2. Pharmacodynamic Statistical Summary

The PD parameters (such as change from baseline of BGmax, BGmax, AUC parameters, and TBGmax) will be summarized using standard descriptive statistics.

Evaluable PD data are defined as having baseline and at least 1 postbaseline measure. For rescued participants, data after the rescue would be excluded from the analysis.

See Section 9.4.3 for details on the exploratory efficacy objective based on PD parameters.

Exploratory analyses may be performed for other PD parameters as deemed appropriate.

9.4.2.2. Pharmacokinetics

9.4.2.2.1. Pharmacokinetic Parameter Estimation

Glucagon concentration data after NG administration will be analyzed using a population PK approach via nonlinear mixed-effects modeling with the NONMEM software due to limited number of PK samples collected in this study. Model-estimated population PK parameters will be reported. Additional population PK analysis may be performed by combining data from this study with data from other NG studies.

Evaluable PK outcome is defined as having at least 1 postbaseline measure. For rescued participants, data after the rescue would be excluded from the analysis.

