2.3.1.2. Historical Summary of Glucagon Safety

Injectable glucagon

There has been extensive patient exposure to recombinant glucagon with injectable administration for approximately 20 years. Side effects noted are generally mild and include nausea and vomiting. Generalized allergic reactions, including urticaria, respiratory distress, and hypotension, have been reported in patients who received glucagon by injection. It is contraindicated in patients with known hypersensitivity to it, or in patients with known pheochromocytoma or insulinoma.

Inclusion and exclusion criteria in this study were designed to mitigate these risks.

Nasal glucagon

NG was approved in the US and Europe in 2019 for the emergency treatment of severe hypoglycemia in patients with diabetes aged 4 years and above.

The NG development program demonstrated that NG is safe in both adult and pediatric patients aged \geq 4 years. The program included 10 studies in adults (healthy subjects and patients with diabetes) and 2 studies in pediatric patients with T1D. This program demonstrated that NG has a comparable safety profile to recombinant glucagon, with the exception of additional effects related to its nasal route of administration. The most commonly reported AEs in the NG development program were vomiting, headache, nausea, and "upper respiratory tract irritation" (rhinorrhea, nasal discomfort, nasal congestion, cough, and epistaxis), watery eyes, redness of eyes, sneezing, and itchy nose, throat, and eyes.

The NG formulation in Study IGBO is the commercial drug product, which was also used in adult Studies I8R-MC-IGBI and I8R-MC-IGBJ. Study IGBI was a multi-center, randomized, open-label, 2-treatment, 2-period, single-dose, crossover study in adult patients with T1D that compared glucagon administered through either the nasal route (NG) or the intra-muscular route (GlucaGen) in the recovery from hypoglycemia induced by a controlled insulin infusion. Study IGBJ was a Phase 3, multi-center, randomized, open-label, active comparator, single-dose, 2-period, 2-treatment, crossover study of NG (LY900018) compared to intramuscular glucagon for treatment of insulin-induced hypoglycemia in adult Japanese patients with diabetes mellitus.

Summary of NG safety in pediatric patients

NG was assessed in pediatric patients in Studies I8R-MC-IGBB and I8R-MC-B001 (B001). In total in these studies, 58 patients aged 4 to <18 years received at least 1 dose of NG.

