10.3 Pharmacokinetic Assessment

10.3.1 Pharmacokinetic Analysis

Glucagon concentration data after NG administration will be analyzed using a population PK approach via nonlinear mixed-effects modeling with the NONMEM software due to limited number of PK samples collected in this study. Model-estimated population PK parameters will be reported. Additional population PK analysis may be performed by combining data from this study with data from other NG studies.

Evaluable PK outcome is defined as having at least 1 postbaseline measure.

Pharmacokinetic concentrations of plasma glucagon by timepoint will be summarized by descriptive statistics and listed. Mean and individual concentration over time plots will also be produced.

Derivation of the PK parameters will be done by Eli Lilly and Company. Eli Lilly and Company will also be responsible for all PK parameter TFLs.

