10.3.2 Pharmacokinetic Statistical Methodology

No inferential statistical analyses are planned

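### Does the PK endpoint need a mandatory combined analysis because three samples per child in at least 6 evaluable children are too few for a stand-alone population model?

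*Protocol*

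**What the plan says.** Protocol Section 3 and SAP 5.2 list one PK endpoint, the model-estimated population parameters. The Schedule of Activities (Protocol 1.3) takes plasma glucagon at 10, 30 and 60 minutes after dosing, and Protocol Appendix 6 confirms three PK samples per child.

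Protocol 9.4.2.2.1 and SAP 10.3.1 both commit to nonlinear mixed-effects modeling in NONMEM and give the small number of samples as the reason. On what comes out, SAP 10.3.1 says "Model-estimated population PK parameters will be reported". On other data, the Protocol says "Additional population PK analysis may be performed by combining data from this study with data from other NG studies", and SAP 10.3.1 repeats this. Neither document names a structural model, a fixed parameter, a prior or a weight covariate, or says which fit supplies the endpoint.

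Other provisions bear on the point:

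- **Size** (Protocol 9.2): "At least 9 participants with an approximate maximum of 20 may be enrolled so that 6 evaluable participants complete the study".
- **PK analysis set** (Protocol 9.4): "data from all enrolled participants who receive the study drug and have evaluable PK or PD data". One postdose sample makes a child evaluable (Protocol 9.4.2.2.1).
- **Observed data** (SAP 10.3.1): "Pharmacokinetic concentrations of plasma glucagon by timepoint will be summarized by descriptive statistics and listed".
- **Responsibility** (SAP 10.3.1): the parameters and all PK parameter tables, figures and listings belong to the sponsor, not to the organization that wrote the SAP.
- **Inference** (SAP 10.3.2): "No inferential statistical analyses are planned".

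**The concern.** Read literally, the plan separates a committed analysis from an additional one that may be performed. The natural inference is that the committed model uses this study's concentrations only. A one-compartment model with first-order absorption has seven parameters: ka, CL/F, V/F, a between-child variance for each, and a residual variance. Eighteen concentrations are thin support for seven parameters, and three times per child say little about the rise of the curve.

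The reported ka and variances could then be nearly uninformative. Because the documents do not say what is estimated, fixed or borrowed, that choice could also be made after the concentrations are seen. Protocol 4.3 expects higher glucagon exposure in this age group than in older children, so a reader would look to the PK endpoint to describe that exposure. The obvious remedy would be to make the combined analysis mandatory.

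**Working it through.** **1. The plan's own figure.** Six evaluable children with 33% dropout (Protocol 9.2): 6 / (1 − 0.33) = 8.96, rounded up to 9. This matches the stated minimum enrollment.

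**2. Data available.** With three samples per child: 6 × 3 = 18, 9 × 3 = 27 and 20 × 3 = 60 concentrations if fully sampled.

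**3. Between-child variances.** Even if each child's parameters were known exactly, the RSE of a variance is about √(2/N). This needs no PK assumption.

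| N | √(2/N) |
|---|---|
| 6 | 58% |
| 9 | 47% |
| 20 | 32% |

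At N = 6 the 95% interval for a variance, on 5 degrees of freedom, runs from 5/12.83 = 0.39 to 5/0.831 = 6.0 times the estimate.

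**4. Typical parameters, if all are estimated from this study alone.** The documents give no PK values, so everything here is assumed: the one-compartment model above, samples at 10, 30 and 60 minutes, 50% between-child SD and 30% residual error. The method is first-order population Fisher information on log concentration. It is asymptotic and therefore optimistic at small N. RSEs at N = 6:

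| ka, kel (per h) | ka | CL/F | V/F | Cmax | AUC 0–60 min |
|---|---|---|---|---|---|
| 8, 1.2 | 60% | 26% | 33% | 19.8% | 16.6% |
| 4, 1.2 | 95% | 43% | 73% | 20.2% | 17.6% |
| 12, 2 | 64% | 22% | 27% | 20.5% | 17.0% |
| 3, 1.5 | 169% | 46% | 147% | 20.5% | 18.0% |

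RSEs scale with √(6/N). For ka this gives 60 × 0.816 = 49% to 169 × 0.816 = 138% at N = 9, and 60 × 0.548 = 33% to 169 × 0.548 = 93% at N = 20.

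A wider grid has 48 scenarios: absorption and elimination half-lives of 5 to 30 minutes in unequal pairs, between-child SD 0.3 or 0.5, residual SD 0.15 or 0.3. At N = 6 the ka RSE runs from 15% to 497%, median 49%, and is 30% or less in 12 of 48. Poor precision for ka is likely but depends on kinetics that the documents do not give.

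**5. What pooling would buy.** Assume 36 older children (the number given 3 mg in the earlier pediatric study, Protocol 2.3.1.2), shared ka and variances, and separate CL/F and V/F for ages 1 to <4. At N = 6, with the older children sampled either at the same three times or at an assumed eight, the RSEs over the four kinetic pairs are:

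| Quantity | Stand-alone | Pooled |
|---|---|---|
| ka | 60–169% | 12–64% |
| V/F | 27–147% | 24–62% |
| CL/F | 22–46% | 22–29% |
| ka variance | 226–641% | 49–69% (eight samples), 86–242% (same three) |
| Cmax | 20–21% | 19–20% |
| AUC 0–60 min | 17–18% | 17–18% |

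**6. What pooling would risk.** Take noise-free concentrations with true ka at half or twice the borrowed value, hold ka at the borrowed value and refit. V/F is biased by −41% to +88% and CL/F by −45% to +13%. Cmax moves only −9% to +3% and AUC 0–60 min −3% to +2%. The largest misfit at the three sampling times is 13%, so an overlay of observed on predicted values would rarely reveal the error. A direct comparison of ka would not help much either: at N = 6, even in the most favorable case, ka would have to differ 3.1-fold for 80% power.

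**The case for a change.** The strongest case for a change is that the endpoint's source is left open. The variance floor needs no kinetic assumption. The ka figures are also optimistic, because exchanging ka with the elimination rate and rescaling V/F gives identical concentrations at all three times, so nasal data alone cannot say which rate is absorption. Naming the reported fit in advance would cost a sentence and no blood, and a reader cannot interpret ka or its variance without knowing whether it was estimated, fixed or taken from older children.

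The arithmetic stands, and so does the gap in wording. Three things limit its weight.

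- **The premise is inferred.** Neither document says that all parameters come from this study alone, and neither excludes fixing or priors. Protocol 4.3 refers to a projected maximum exposure for ages 1 to <4, so the sponsor already had some PK projection for this group. Under SAP 10.3.1 the sponsor also owns the derivation, so silence in a SAP written elsewhere is weak evidence that no model exists.
- **Six is the minimum.** A child who is dosed, gives one PK sample and then misses the Day 9 call still contributes.
- **Comparability is unknown.** Protocol 2.3.1.2 says: "The NG formulation in Study IGBO is the commercial drug product, which was also used in adult Studies I8R-MC-IGBI and I8R-MC-IGBJ". The documents do not give the formulation, assay or PK sampling times of the earlier pediatric study. A mandatory pooled analysis would therefore need an escape clause, and that clause leads back to the stand-alone fit.

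**Conclusion.** No change is needed. On the stated assumptions, a model with every parameter estimated from this study alone would give between-child variances no better than 58% RSE at N = 6 (32% at N = 20), and probably an imprecise ka. The plan does not commit to such a model, and the quantities that describe early exposure are little affected: Cmax has an RSE of about 20% and AUC over 0–60 minutes 17–18%, pooled or not.

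Mandatory pooling is a trade-off on which pharmacometricians could reasonably differ. It sharpens ka and V/F, still leaves the ka variance at 49% RSE or worse, and can bias V/F by −41% to +88% with little chance of detection. Leaving it optional until comparability can be judged is a fair choice.

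Nothing downstream depends on the answer. The dose cannot be modified (Protocol 6.6), no PK inference is planned (SAP 10.3.2), and observed concentrations are summarized and listed in any case. What remains is a gap in description. Analysts fill it sensibly by saying in the report which fit supplied the parameters, which were estimated, fixed or borrowed, and with what RSE. The kinetic values and variabilities above are assumed; only the √(2/N) floor is free of kinetic assumptions.

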8.3.6.2. Rescue Procedure

Oral or intravenous glucose or glucagon may be given as appropriate to the clinical situation. If NG was administered, any remaining blood samples will be collected, if possible, according to the SoA.

Further details will be provided to the site in the Study Operations Manual.

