9. DEFINITION OF ANALYSIS POPULATIONS

The "Efficacy" population will consist of all patients who received at least one dose of NG, and have baseline and at least 1 postbaseline PG measure within 30 minutes after dose administration. For rescued patients, data after the rescue would be excluded from the analysis.

The "Safety" population will consist of all patients who received at least one dose of NG, whether or not they complete all protocol requirements.

The "Pharmacokinetic" population will consist of all patients who received at least one dose of NG and have evaluable PK data. For rescued patients, data after the rescue would be excluded from the analysis.

The "Pharmacodynamic" population will consist of all patients who received at least one dose of NG and have evaluable PD data. For rescued patients, data after the rescue would be excluded from the analysis.

All protocol deviations that occur during the study will be considered for their severity/impact and will be taken into consideration when patients are assigned to analysis populations.

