10.6.2 Glucose Monitoring and Hypoglycemia

At baseline, during, and after dosing, blood glucose (BG) levels will be measured at the bedside for safety monitoring using an approved point-of-care glucometer. The bedside glucose measurements will be performed for safety monitoring only and will not be databased.

Severe hypoglycemica in children events will be listed and summarized. Severe hypoglycemia in children is defined³ as follows:

Severe hypoglycaemia in children: because children have limited ability to detect and/or self-treat hypoglycemia, severe hypoglycemia in children is an event in which children have severe cognitive impairment, and require external assistance, are semiconscious or unconscious, or in coma with or without convulsions, and requires another person to actively administer carbohydrates, glucagon, or take other corrective action

The determination of a hypoglycemic event as an episode of severe hypoglycemia, as defined above, will be made by the investigator based on the medical need of the patient to have had hypoglycemia-induced cognitive dysfunction and is not predicated on the report of a patient simply having received assistance.

Further information on patients that experience a hypoglycemic event will be collected using a hypoglycaemia event CRF form, this data will be listed and summarized.

A glucose infusion alternative glucagon therapy, or oral carbohydrate may be used for rescue treatment if a patient's BG level is declining rapidly, or their symptoms become consistent with progression to clinically significant or severe hypoglycemia. A separate listing will be presented for the use of rescue medication used for severe hypoglycaemia.

The following steps will be taken based on the patient's baseline BG level:

- If BG < 70 mg/dL, the investigator will determine whether to proceed with dosing or to use rescue treatment.
- If BG < 54 mg/dL (clinically significant hypoglycemia [Level 2]), site will halt study drug procedure and use rescue therapy to raise BG level. Such patients' visits may be rescheduled for a subsequent visit

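### The PK rule drops glucagon concentrations after any rescue, including glucose or carbohydrate rescue, which adds no glucagon to the samples

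*Protocol*

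**What the plan says.** Protocol Section 9.4.2.2.1 decides which glucagon concentrations are analysed: "Evaluable PK outcome is defined as having at least 1 postbaseline measure. For rescued participants, data after the rescue would be excluded from the analysis". SAP Section 9 forms the Pharmacokinetic population from children who received at least one dose and "have evaluable PK data. For rescued patients, data after the rescue would be excluded from the analysis". Neither text mentions the rescue agent.

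The agent can differ. Protocol Section 8.3.6.2: "Oral or intravenous glucose or glucagon may be given as appropriate to the clinical situation". SAP Section 10.6.2: "A glucose infusion alternative glucagon therapy, or oral carbohydrate may be used for rescue treatment". The same protocol section keeps sampling going after rescue: "If NG was administered, any remaining blood samples will be collected, if possible, according to the SoA".

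The Schedule of Activities places PK samples at 10, 30 and 60 minutes, with none predose. Protocol Section 8.5 puts each at about 2 mL. The PK endpoint is the set of model-estimated population PK parameters. SAP Section 10.3.1 adds descriptive summaries of concentration by timepoint, and mean plots.

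The same post-rescue exclusion applies to PD (Protocol Section 9.4.2.1.2) and to exploratory efficacy (Section 9.4.3). Neither document gives a reason specific to PK.

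**The concern.** For plasma glucose the exclusion has an obvious basis: glucose given as rescue changes the quantity being measured. For plasma glucagon that basis holds only when the rescue agent is glucagon. After glucose or carbohydrate, the remaining samples still measure glucagon without any added by the rescue, yet the rule leaves them out.

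Two things are at stake. The first is information: the plan aims for six evaluable children with three PK samples each, so every excluded concentration counts. The second is possible selection. Under Protocol Section 8.3.6.1 a glucose infusion may be started when glucose falls rapidly or symptoms progress, and Section 2.2 gives raising blood glucose as the principal action of nasal glucagon. A child who received or absorbed little drug is plausibly more likely to be rescued, so the missing concentrations could be the lower ones. Those concentrations would also help to separate poor absorption from other causes of rescue.

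**Working it through.** **1. The plan's own figure.** Protocol Section 9.2 gives six evaluable completers, 33% dropout and at least nine enrolled. 6 / (1 − 0.33) = 8.96, which rounds up to 9. The figure reproduces, and this point does not change it.

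**2. Which rescues affect the assay.** Section 2.2 says nasal glucagon is the same 29-amino-acid peptide as human glucagon and the marketed recombinant products. Section 8.5.1 assays glucagon concentration by liquid chromatography with tandem mass spectrometry. Rescue glucagon would therefore be expected to be counted with the nasal dose, and excluding data after it is justified. Glucose and carbohydrate contain no glucagon.

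**3. Samples lost per glucose-rescued child.** Samples are at 10, 30 and 60 minutes, so N children give 3N.

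| Time of glucose rescue | Lost of 3 | PK blood (2 mL each) | N = 6 (18) | N = 9 (27) | N = 20 (60) |
|---|---|---|---|---|---|
| Before 10 min | 3 | 6 mL | 16.7% | 11.1% | 5.0% |
| 10 to 30 min | 2 | 4 mL | 11.1% | 7.4% | 3.3% |
| 30 to 60 min | 1 | 2 mL | 5.6% | 3.7% | 1.7% |
| After 60 min | 0 | 0 mL | 0% | 0% | 0% |

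Two such children among six double the losses, to 11.1% to 33.3%. In the first row no postbaseline concentration is retained, so the child is not PK-evaluable. If that child is replaced to restore six, 3 of 21 samples are lost (14.3%). At the interim after three completers, the first row is 3 of 9 (33.3%).

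**4. Under an agent-specific rule.** A glucose or carbohydrate rescue costs 0 of 18 samples in the main analysis.

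**5. How large a bias could be.** The documents give no rescue rate and no between-child variability, so only an assumed range is possible. Take lognormal concentrations at one timepoint in six children, and suppose the excluded children are exactly those with the lowest values (200,000 simulated sets).

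| Assumed CV | Geometric mean, lowest 1 dropped | Lowest 2 dropped |
|---|---|---|
| 30% | +8% | +15% |
| 60% | +15% | +30% |
| 90% | +22% (1.215) | +44% |

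If exclusion is unrelated to concentration, the shift is about 0%. This concerns a by-timepoint summary under complete selection. It does not estimate bias in the population PK parameters.

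**The case against.** A reader might infer that the rule removes low-exposure children and so inflates the PK endpoint by a calculable amount. For example, if one of six children is excluded with 0 to 50% of the others' exposure, the arithmetic mean rises by 6/5 − 1 = 20% down to 6/5.5 − 1 = 9%. The documents do not support that reading, for four reasons.

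- **Selection is not established.** Glucose may fall for other reasons: insulin may be given before dosing (Protocol Section 4.1.4), and dosing below 70 mg/dL is left to the investigator (Section 8.3.6.1). Section 4.3 expects exposure high enough to produce the maximum glucose effect, so glucose response need not track exposure.
- **The statistic is not the endpoint.** The endpoint comes from a nonlinear mixed-effects model. A child with one retained sample stays in it, and data may be pooled with other studies.
- **The denominator can change.** SAP Section 8 allows replacement of a child without a postbaseline PD measure, and a child rescued before 10 minutes would retain none. With seven dosed, the same assumptions give 7/6 − 1 = 17% down to 7/6.5 − 1 = 8%.
- **Rescue may be rare.** Hypoglycemia is not induced, and the baseline target is 70 to 140 mg/dL. A baseline below 54 mg/dL halts the study drug procedure, so rescues on that ground involve no PK samples.

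Nor are the data lost from view. SAP Sections 10.1 and 10.3.1 list them, and supplementary analyses are permitted. It can also be argued that one conservative rule across PK, PD and efficacy is a reasonable simplification in a descriptive study. Glucose might also alter the child's own glucagon, and without a predose PK sample this cannot be checked.

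All of this limits the claim about bias. None of it gives a reason to exclude concentrations after glucose rescue from the main analysis. The model does not protect a child with no retained sample, and the by-timepoint summaries have no model protection at all. Uncertainty about endogenous glucagon is better handled by a sensitivity analysis than by blanket exclusion.

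**Conclusion.** The point stands as a defect in the analysis rule. As written, both documents leave concentrations after a glucose or carbohydrate rescue out of the population PK model and the by-timepoint summaries, although that rescue adds no glucagon. The cost is one to three of a child's three samples per rescued child. A child given glucose before 10 minutes contributes nothing to the PK analysis, even with all three samples drawn.

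Upward bias in exposure is possible and its direction is plausible, but it rests on an inference from the rescue trigger. Its size on the population PK parameters cannot be derived from the documents. The effect is nil if no child receives a glucose or carbohydrate rescue between dosing and the 60-minute sample. The exclusion remains right after a glucagon rescue, and for plasma glucose.

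**What to change.** In Protocol Section 9.4.2.2.1 and in the Pharmacokinetic population of SAP Section 9, make the exclusion depend on the agent:

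- Exclude glucagon concentrations from the PK analysis only from the time of a glucagon rescue.
- Keep concentrations after glucose or carbohydrate rescue, and flag them in listings and in the modelling dataset.
- Add a sensitivity analysis that excludes the flagged concentrations, because endogenous glucagon may change and there is no predose PK sample.
- Leave the post-rescue exclusion in place for plasma glucose, in both PD and efficacy.

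The cost is about one sentence in each document and one extra model run and summary if any such rescue occurs. No new samples are needed: Protocol Section 8.3.6.2 already continues sampling where possible. Section 6.5 already requires medications to be recorded in the eCRF, and the existing rule already depends on knowing when rescue was given. The change affects the analysis only, not how children are managed.
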